#### **5.3.1. Definition of Endpoint(s)**

The primary endpoint is the change in RVSV from baseline to Week 26 as assessed by pulmonary artery flow MRI:

$$\text{RVSV at Week 26} - \text{RVSV at baseline}$$

The baseline reference values for RVSV is based on the RVSV as determined from the screening MRI.

#### **Handling of missing data**

By design, only one post-baseline RVSV measurement will be taken at the time of the scheduled Week 26 or at the premature EOT visit.

In some instances, the Week 26 (or premature EOT) assessment may be missing with no other post-baseline assessment available.

No imputation methods will be used for the primary endpoint analysis.

### **5.3.2. Analysis Methods**

Due to very limited number of subjects, the absolute values at baseline and post-baseline as well as the absolute changes from baseline to post-baseline in RVSV will be reported in an individual subjects' listing on the SS. No imputation will be performed.

### **5.4. Secondary Endpoint(s) Analysis**

Due to the small sample size, only listings will be provided for all secondary endpoints on the SS. No imputation of missing data will be performed.

#### **5.4.1. Change from baseline to Week 26 of additional measures of RV function using MRI**

Change from baseline to Week 26 assessed by MRI for:

- RV end-diastolic volume (RVEDV)
- RV end-systolic volume (RVESV)
- RV ejection fraction (RVEF)
- RV mass
- RV global longitudinal strain (RVGLS).

The change from baseline to Week 26 for these additional measures of RV function assessed by MRI will be listed by timepoint on the SS.

#### **5.4.2. Change from baseline to Week 26 for 6MWD, WHO FC and NT-proBNP**

Absolute values as well as the change from baseline to Week 26 in 6MWD will be reported in individual subjects' listing on the SS.

WHO FC will be listed on the SS by timepoint. Changes from baseline in WHO FC will be dichotomized as worsening (i.e., change  $>0$ ) versus no change or improvement (ie, change  $\leq 0$ ) and reported in the listing.

NT-proBNP will be listed on the SS by timepoint on the SS

#### **5.4.3. Change from baseline to Week 26 in the number of low-risk criteria**

The change from baseline to Week 26 in the number of low-risk criteria based on the following 8 variables in accordance with the 2015 ESC/ERS Guidelines for the diagnosis and treatment of pulmonary hypertension:

- Absence of clinical signs of right heart failure (“Does the patient have clinical signs of right heart failure?” = ‘No’ in the ‘Risk Stratification’ eCRF form)
- Absence of symptoms of PAH progression (“Progression of PAH symptoms” = ‘No’ in the ‘Risk Stratification’ eCRF form)

- Absence of syncope (“Did the patient experience syncope?” = ‘No’ in the ‘Risk Stratification’ eCRF form)
- WHO FC I-II
- 6MWD >440m
- NT-proBNP < 300 ng/L
- Right atrial (RA) area <18 cm^2, as determined by Echo
- Absence of pericardial effusion, as determined by Echo

will be calculated for each participant in the SS, and reported in a listing. The number of low-risk criteria at baseline and Week 26 constitutes the risk score and will be derived for each subject by adding ‘1’ for each of the above criteria met. The number of low-risk criteria for each subject can vary from 0 (worse subjects) to 8 (healthier subjects). Note: the risk score will be assessed excluding subjects with even a single missing value at baseline and/or endpoint visit.

## **5.5. Tertiary/Exploratory Endpoint(s) Analysis**

Due to the small sample size, only listings will be provided for all exploratory endpoints.

### **5.5.1. Change from baseline to Week 52 on RV function assessed by MRI**

The absolute values as well as the change from baseline to Week 52 in RVSV, RVEDV, RVESV, RVEF, RV mass and RVGLS assessed by MRI will be listed on the SS.

The number and percent of participants who achieve normalized RVSV at Week 26 and Week 52 will be displayed in the above listing. Patients with a RVSV >60mL will be considered as normal (Kawel-Boehm, 2015), this is consistent with Protocol inclusion criterion 4.2.

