5.1. Inclusion Criteria

Each potential participant must satisfy all of the following criteria to be enrolled in the study:

1. Signed informed consent prior to any study-mandated procedure.
2. Criterion modified per Amendment 2
 - 2.1 WHO FC II or III. Enrollment will be stratified by WHO FC II or III. Proportion of participants with WHO FC II and WHO FC III are expected to be approximately 40% and 60%, respectively.
3. Criterion modified per Amendment 2
 - 3.1 PAH etiology belonging to one of the following groups according to classification²⁷:
 - Idiopathic PAH
 - Heritable PAH
 - Drugs or toxins induced
 - PAH associated with connective tissue disease
 - PAH associated with congenital heart disease, with simple systemic-to-pulmonary shunt at least 1 year after surgical repair.
4. Criterion modified per Amendment 2
 - 4.1 Criterion modified per Amendment 3
 - 4.2 Diagnosis of PAH within 3 years prior to initiation of selexipag (Day 1), and most recent right heart catheterization (RHC) within 1 year prior to initiation of selexipag (Day 1) showing:
 - mPAP \geq 25 mmHg and
 - PA wedge pressure (PAWP) or LV end-diastolic pressure (LVEDP) \leq 15 mmHg and
 - PVR $>$ 5 WU (400 dyn.s.cm⁻⁵) and
 - RVSV \leq 60 mL as shown in RHC.
5. Criterion modified per Amendment 2
 - 5.1 Patients already receiving PAH-specific oral mono or dual therapy (ie, phosphodiesterase type 5 inhibitors (PDE-5i) or soluble guanylate cyclase stimulators (sGCs) and/or ERA) or patients who are not candidates for these therapies. If on oral PAH-specific therapy, treatment has to be stable (ie, no introduction of new therapies or changes in dose) for at least 90 days prior to both ICF signature and Day 1.
6. Criterion modified per Amendment 2
 - 6.1 Criterion modified per Amendment 3
 - 6.2 NT-proBNP \geq 300 ng/L (\geq 300 pg/mL; \geq 35.5 pmol/L) at screening. Note: If local assessment of BNP (instead of NT-proBNP) is used for eligibility, BNP measurement of \geq 50 ng/L (\geq 50 pg/mL; 14.4 pmol/L) will be considered as meeting the inclusion criterion.
7. Criterion modified per Amendment 2

7.1 Men or women ≥ 18 years (or the legal age of consent in the jurisdiction in which the study is taking place if greater than 18) and <65 years.

8. Criterion modified per Amendment 2

8.1 Criterion modified per Amendment 3

8.2 Women of childbearing potential (Section 10.5) must meet the following criteria:

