8.3.1.5. Imaging Assessment

After an individual participant's Week 26 or Week 52 imaging assessments, a single reviewer will read all scans (MRI or Echo) of that participant at once. For this review, expert reviewers will be blinded to the participant and timepoint and will assess variables according to the MRI/Echo review charter.

8.3.2. 6MWT

Exercise capacity will be measured by the 6MWT. The 6MWT is a non-encouraged test that measures the distance walked in 6 minutes. It will be performed according to sponsor guidance (Section 10.9).

At Week 26 and EOT visit, participants must NOT take the morning study intervention dose before any visit-related procedure.

Dyspnea will be assessed by the Borg CR 10 Scale®, a scale used to quantify the degree of shortness of breath before and at the end of the 6MWT (Section 10.9).

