**6.2. Appendix 2 Changes to Protocol-Planned Analyses**

- The number and percent (%) of patients achieving a normalized RVSV assessed by MRI at Week 26 and Week 52 was added as an exploratory endpoint.
- Following premature study termination, it is clarified that only descriptive statistics will be reported, no analysis will be performed using FAS/PP and no subgroup analysis will be performed.

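### The count of participants who reach a normal RVSV has no baseline condition, so someone already above 60 mL on the screening MRI can be counted

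*SAP*

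**What the plan says.** SAP 5.5.1 states: "The number and percent of participants who achieve normalized RVSV at Week 26 and Week 52 will be displayed in the above listing". The cut-off follows: "Patients with a RVSV >60mL will be considered as normal". The SAP supports it with a literature reference and the remark that "this is consistent with Protocol inclusion criterion 4.2".

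SAP Appendix 2 (6.2) confirms that the measure is by MRI and is new in the SAP: the number and percent of "patients achieving a normalized RVSV assessed by MRI at Week 26 and Week 52 was added as an exploratory endpoint". The protocol therefore contains no further definition of it.

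Three other places bear on baseline status:

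- SAP 5.3.1, on baseline RVSV: "The baseline reference values for RVSV is based on the RVSV as determined from the screening MRI".
- Protocol 5.1, criterion 4.2, requires RVSV of at most "60 mL as shown in RHC". The catheterization concerned is the most recent one, within 1 year before Day 1.
- SAP 5.1.3 excludes participants who have no baseline value from the corresponding analysis.

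**The concern.** The label describes a transition: a participant moves from an abnormal value to a normal one. The written rule describes a state at the visit, namely MRI RVSV above 60 mL. The two agree only if every participant starts at or below 60 mL on MRI, and nothing in the plan ensures that.

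The reference to criterion 4.2 may lead a reader to assume that it does. If it does not, the reported percentage mixes participants who crossed the threshold on treatment with participants who were never below it on the study's own measurement. Two programmers could also produce different counts from the same data, one following the label and the other the rule.

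**Working it through.** The plan gives no figure for this endpoint, so the check is mainly a comparison of texts.

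**1. The rule as written.** Counted at a visit if MRI RVSV at that visit > 60 mL. Baseline does not appear in it. Example: baseline 75 mL, Week 26 65 mL. The change is 65 − 75 = −10 mL, and 65 > 60, so the participant is counted.

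**2. Could such a participant be in the study?** Four possible barriers were checked.

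| Possible barrier | What it covers | Closes the gap? |
|---|---|---|
| Protocol 5.1, criterion 4.2 | RVSV by catheterization, up to 1 year before Day 1 | No: different method, different date |
| Other criteria in Protocol 5.1 and 5.2 | None limits MRI RVSV; the only entry value that may come from cardiac MRI is left atrial volume (exclusion 8) | No |
| Central MRI reading, Protocol 8.3.1.5 | After a participant's "Week 26 or Week 52 imaging assessments, a single reviewer will read all scans (MRI or Echo) of that participant at once" | No: the central baseline value does not exist at entry |
| SAP 5.1.3 | Missing baseline values only | No |

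A baseline MRI RVSV above 60 mL is therefore compatible with every stated rule.

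**3. Effect of one such participant.** The counts are assumed, because the documents give none. Removing one participant who was above 60 mL at both times takes one from the numerator and one from the denominator:

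- 2/5 = 40% becomes 1/4 = 25%
- 4/10 = 40% becomes 3/9 = 33%

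**4. How many could there be?** The documents give neither the distribution of baseline MRI RVSV nor the agreement between catheterization and MRI. The following is an illustration with every input assumed. Let the catheterization value x be normal with mean 40, 45, 50, 55 or 60 mL and SD 12 or 15 mL, truncated to 20–60 mL with density f(x). Let the MRI value differ from x by a normal error with mean *shift* and standard deviation SD. Then

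P(baseline MRI > 60) = ∫ from 20 to 60 of f(x) · [1 − Φ((60 − x − shift)/SD)] dx

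| SD of difference (mL) | Shift −5 mL | Shift 0 | Shift +5 mL |
|---|---|---|---|
| 5 | 0.5–2.7% | 2.8–12.6% | 8.7–32.7% |
| 10 | 3.4–11.5% | 7.5–22.1% | 14.3–36.6% |
| 16.34 | 9.4–20.8% | 14.6–29.9% | 21.5–40.3% |
| 20 | 13.0–24.8% | 18.4–32.8% | 25.0–41.8% |

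The values 16.34 and 20 mL are SDs of 26-week change taken from Protocol 9.2. They do not measure agreement between the two methods and serve only as wide settings. The overall range, 0.5% to 42%, is too broad to grade the point, and the grade does not rest on it.

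**The case against.** The cited sentence defines what counts as normal. It does not say what it means to reach normal. In ordinary use a participant who goes from 75 to 65 mL was never abnormal and has not normalized, so a transition reading is available. The remark about criterion 4.2 most naturally says that the same 60 mL threshold was used at entry, and it makes no claim about MRI baseline. The count appears with a listing of individual values and changes, and SAP 5.3.2 also lists baseline RVSV, so any affected participant is visible. No hypothesis, inference or decision depends on the percentage. Reporting the share above 60 mL at the visit is itself a legitimate description if it is labelled that way.

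Much of this stands. The transition reading is possible, the criterion 4.2 remark is not a false statement, and the consequence is small. The timing of the central read is secondary too, since no criterion would have used an MRI RVSV value in any case. What does not follow is that the definition is adequate. The only operational rule omits baseline, and the label and the rule can give different counts. The SAP also asks for a number and a percentage, which can be quoted apart from the rows beneath them. Visible baseline values let a careful reader correct the figure, but they do not define it.

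**Conclusion.** The concern holds, as a minor point. As written, SAP 5.5.1 can count a participant already above 60 mL on the baseline MRI as having normalized, and no eligibility or baseline rule excludes that case. This conclusion rests on the text alone. How many participants are affected is unknown and may be zero. The 40% to 25% and 40% to 33% shifts use assumed counts and show only that one case can matter where the SAP itself refers to a very limited number of subjects. The early termination, the restriction of efficacy to listings, the absence of inference and the display of individual values keep the impact low.

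**What to change.** In SAP 5.5.1, define a participant as normalized at Week 26 (or Week 52) only if baseline MRI RVSV is ≤60 mL and MRI RVSV at that visit is >60 mL. Take the percentage over Safety Set participants with baseline MRI RVSV ≤60 mL and a value at that visit. Add a baseline flag (≤60 / >60 mL) to the listing. A short note that criterion 4.2 is a catheterization value and does not establish MRI baseline status would help but is optional.

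If the sponsor prefers to report the state at the visit, the alternative is to relabel the count as the number with RVSV above 60 mL at that visit and drop the wording that implies a change.

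The main fix takes two sentences and one listing flag, all from data already collected. Its cost is a smaller denominator in an already very small set, and possibly a lower percentage.

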### **5.5.2. Change from baseline to Week 26 and Week 52 of RV mass/LV mass**

The absolute values as well as the change from baseline to Week 26 and Week 52 in RV mass/LV mass assessed by MRI will be listed on the SS.

### **5.5.3. Change from baseline to Week 26 of RV function assessed by Echo**

The absolute value as well as the change from baseline to Week 26 of RV function assessed by Echo for the parameters listed below, will be listed on the SS:

- Tricuspid annular plane systolic excursion (TAPSE)
- Pericardial effusion size scored from 0 to 4
- RV end-diastolic area
- RV end-systolic area
- RV fractional area change
- RVSV determined from pulmonary valve Doppler and pulmonary annulus dimension

- RA area.

#### **5.5.4. Change from baseline to Week 26 and Week 52 of LV function assessed by MRI**

The absolute values as well as the change from baseline to Week 26 and Week 52 of LVEDV, LVESV, LV ejection fraction and LV mass assessed by MRI will be listed on the SS.

#### **5.5.5. Change from baseline to Week 26 and Week 52 of Right main PA pulsatility assessed by MRI**

The absolute values as well as the change from baseline to Week 26 and Week 52 of right main PA pulsatility assessed by MRI will be listed on the SS.

#### **5.5.6. Change from baseline to Week 26 and Week 52 of RV/LV function using 4D flow imaging**

The absolute values as well as the change from baseline to Week 26 and Week 52 of RVSV determined from 4D flow imaging in PA and LVSV determined from 4D flow imaging in aorta, in participants from sites able to provide suitable MRI imaging, will be reported in individual subjects' listing on the SS.

#### **5.5.7. Impact of individual maintenance dose**

Due to the very limited number of patients, RVSV will not be analyzed by maintenance dose subgroup.

#### **5.5.8. Change from baseline to Week 52 for 6MWD, WHO FC and NT-proBNP**

The change from baseline to Week 52 for 6MWD, WHO FC and NT-proBNP will be analyzed similarly as the change from baseline to Week 26 in Section [5.4.2](#).

#### **5.5.9. EuroQol 5-dimension scale (EQ-5D-3L)**

The health profile and health state index score will be derived according to the instrument's instruction for each individual and visit. The absolute values as well as the change from baseline to Week 26 and Week 52 in the health profile, in the health state index score and in the EQ VAS will be reported in a listing on the SS.

#### **5.5.10. Change from baseline to Week 26 and Week 52 in the difference between the pre-walk and post-walk assessed Borg Dyspnea Index (BDI)**

The pre-walk assessed BDI and post-walk assessed BDI at Week 26 and Week 52 as well as the difference between the pre-walk and post-walk assessed BDI at both visits and from baseline will be listed on the SS.

### **5.6. Safety Analyses**

All safety analyses will be conducted on the safety analysis set.

For all continuous safety variables, descriptive statistics will include the N, mean, standard deviation, median, minimum, and maximum. Categorical variables will be summarized using frequency counts and percentages.

### **5.6.1. Extent of Exposure**

Exposure will be summarized up to EOT.

The number and percentage of participants who received study intervention will be summarized.

Descriptive statistics for duration of study intervention (N, mean, SD, median, and range (minimum, maximum)) will be summarized. Participant-years of intervention are calculated as [days of intervention/365.25].

Duration of exposure will be summarized in the following duration categories: <1 week, 1-<4 weeks, 4-<12 weeks, 12-<26 weeks,  $\geq$  26 weeks.

Cumulative duration of intervention  $\geq$  1 week,  $\geq$  4 weeks,  $\geq$  12 weeks,  $\geq$  26 weeks will be summarized.

Study intervention duration is defined as (date of last dose of study intervention – date of first dose of study intervention) +1.

Total dose days of intervention is defined as the total number of days that study intervention was administered to the participant (excluding days off study intervention).

The number (%) of participants with a dose adjustment/dose not administered will be summarized. Reasons for dose adjustments/doses not administered will also be summarized.

Descriptive statistics will be presented for the following parameters during the dose maintenance period:

- The number (%) of participants with a dose adjustment after the 12-week up-titration period. Reasons for dose adjustments will also be summarized.
- Cumulative total dose per participants
- Mean daily dose per participant (after the 12-week up-titration period)
- IMD at end of Week 12 (Day 84).

The mean daily dose of study intervention is calculated as (sum of total daily dose)/study treatment duration.

The total daily dose is calculated according to frequency and dose ( $\mu$ g).

Frequency (coded) a	Total daily dose (µg / day)
Once a day	dose
Twice a day	2 × dose
Twice weekly	2 × dose / 7
Monthly	dose / 30.5
Every other day	dose / 2
<X> times	<X> × dose
<X> times	<X> × dose / 7
Weekly	dose / 7
Every <X>	dose /(7 × <X>)
Twice per month	2 x dose / 30.5
Missing, other codes	0

a: values coded to CONTINUOUS, ONCE, AS NECESSARY, INFREQUENT, UNKNOWN cannot be used to determine the total daily dose and therefore the total daily dose will be set to zero.

The cumulative total dose per participant is calculated as the sum of total daily dose over the whole treatment period.

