Unscheduled visits: Unscheduled visits will be allowed and will not be documented in the electronic case report form (eCRF); however, any AE/SAE reported during an unscheduled visit should still be recorded.

Eligible participants will be treated with selexipag for 52 weeks. Dosing with selexipag will start at 200 µg twice daily. On Day 1, the participant will receive only 1 dose, and at each dose change, the first intake of the new dose should be taken in the evening. The site will call the participant once a week from the end of Week 1 to the end of Week 12 and decide whether to increase the dose by 200 µg twice daily if possible. Up-titration will be flexible and can be adapted in case of adverse effects that cannot be relieved with symptomatic treatment. In this case, the site may either postpone up-titration by 1 week or down-titrate study intervention. The dose reached at end of Week 12 will be considered the participant's IMD and will be maintained until EOT.

Efficacy assessments will include MRI, Echo, 6MWT, WHO FC, NT-proBNP, and risk stratification. Safety assessments will include the monitoring of AEs, clinical laboratory evaluations, and pregnancy testing in female participants of childbearing potential. Exploratory assessment will include biomarkers and the participants' experience using a questionnaire.

A diagram of the study design is provided in [Figure 1](#).

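### SAP 5.6.1 counts a positive dose as no drug when its frequency is missing, UNKNOWN or ONCE, so any such record left after querying understates that participant's exposure

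*SAP*

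**What the plan says.** SAP 5.6.1 (Extent of Exposure) converts each study drug record into a total daily dose from the recorded dose and a coded frequency. Once a day gives the dose and twice a day gives twice the dose. The last row of the conversion table, "Missing, other codes", gives 0. The table's footnote adds that the codes CONTINUOUS, ONCE, AS NECESSARY, INFREQUENT and UNKNOWN "cannot be used to determine the total daily dose and therefore the total daily dose will be set to zero".

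Two summaries use these values:

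- Mean daily dose: "The mean daily dose of study intervention is calculated as (sum of total daily dose)/study treatment duration". Study intervention duration is defined in the same section as calendar days from first to last dose, both included. The listed summary is the post-titration mean.
- Cumulative dose: "The cumulative total dose per participant is calculated as the sum of total daily dose over the whole treatment period".

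SAP 5.6.1 gives no other derivation for affected records, no exclusion, no count of them and no sensitivity summary.

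Protocol 4.1 says "On Day 1, the participant will receive only 1 dose". Planned dosing is otherwise twice daily (Protocol 6.1), or once daily for a defined subgroup (Protocol 6.2 and 6.7). Protocol 7.2 requires interruptions of a day or longer to be entered on the study intervention log.

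**The concern.** A positive dose with an unreadable frequency means that drug was taken in an uncertain amount. The rule turns this into a definite statement that none was taken. The planned frequencies are once or twice daily, so the plausible amount is one or two times the recorded dose, and zero lies outside that range.

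For ONCE there is no uncertainty to resolve, since the amount is one administration.

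The rule also makes a data gap look like a true interruption. Within SAP 5.6.1 it can contradict the count of days on which drug was given: a day can count as a dosing day and still carry 0 µg.

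What is at stake is the accuracy of the reported exposure. SAP 5.3.2 describes the number of subjects as very limited, and the safety summaries print a minimum (SAP 5.6). One affected participant could set that minimum and visibly move the mean.

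**Working it through.** The plan states no exposure figure, so there is nothing to reproduce. The check applies the SAP 5.6.1 formulas to the schedule in Protocol Table 2.

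**Inputs**
- Protocol Table 2: 200 µg twice daily in Week 1, rising by 200 µg weekly to 1,600 µg in Week 8. Maintenance is Days 85 to 364, which is 280 days.
- Day 1: a single 200 µg dose.
- Assumed: full intake for 52 weeks, and 7, 28 or 91 maintenance days with an unresolved frequency. The documents give no rate for this.
- Assumed: the post-titration mean uses maintenance days in both numerator and denominator.
- Simplification: each dose change is counted from the morning. Starting each new dose in the evening would remove 200 µg at each of 7 steps, or 1,400 µg in all (0.13% of the total below).

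**Correct totals, maintenance dose 1,600 µg twice daily**
- Days 1 to 7: 200 + 6 × 400 = 2,600 µg.
- Weeks 2 to 8: 7 × 2 × (400 + 600 + 800 + 1,000 + 1,200 + 1,400 + 1,600) = 98,000 µg.
- Days 57 to 364: 308 × 3,200 = 985,600 µg.
- Cumulative dose: 1,086,200 µg. Maintenance mean: 896,000 / 280 = 3,200 µg/day.

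**Correct totals, maintenance dose 200 µg twice daily**
- Cumulative dose: 200 + 363 × 400 = 145,400 µg. Maintenance mean: 400 µg/day.

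**Under the zero rule**, with k affected maintenance days, the mean becomes (280 − k)/280 of its true value at any constant dose. Cumulative dose loses k × daily dose.

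| k | Fall in post-titration mean | Mean at 1,600 µg twice daily (µg/day) | Fall in cumulative dose, 1,600 µg twice daily | Fall in cumulative dose, 200 µg twice daily |
|---|---|---|---|---|
| 7 | 2.5% | 3,120 | 22,400 µg (2.1%) | 2,800 µg (1.9%) |
| 28 | 10% | 2,880 | 89,600 µg (8.2%) | 11,200 µg (7.7%) |
| 91 | 32.5% | 2,160 | 291,200 µg (26.8%) | 36,400 µg (25.0%) |

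**Day 1 coded ONCE:** 200 / 1,086,200 = 0.02%, and 200 / 145,400 = 0.14%. Day 1 is not a maintenance day, so the post-titration mean does not change.

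**Zero against the plausible range, k = 28 at 1,600 µg.** The zero rule gives 1,086,200 − 89,600 = 996,600 µg. Counting the recorded dose once daily gives 996,600 + 28 × 1,600 = 1,041,400 µg, and twice daily gives 1,086,200 µg. The reported value lies below both.

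**Effect of removing the days.** The mean is repaired: 252 × 3,200 / 252 = 3,200 µg/day. The cumulative sum stays at 996,600 µg, exactly as under the zero rule, so it needs separate handling.

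**The case against.** The strongest reply is that the error may never arise. The conversion table looks like a general-purpose code list, since it has monthly and twice-weekly rows for a drug given once or twice a day. Protocol 10.3.8 and 10.3.9 already provide for completeness review and data queries, so the zero rule is a fallback for what remains. If no positive-dose record keeps an affected code, the bias is zero. This stands: the point is conditional.

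Three stronger readings are tempting, and the documents do not support them:

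- A reader might infer that exposure will be materially understated, by a quarter or more. That needs something like a 91-day record with no usable frequency. The documents give neither such a record nor a rate of missing frequencies.
- A reader might infer that the single Day 1 dose makes ONCE a systematic problem. The eCRF code list is not shown, and the loss would be only 200 µg.
- A reader might infer that the safety and efficacy results are affected. No planned analysis uses these values. Efficacy is listings only (SAP 5.1), the analysis by maintenance dose is dropped (SAP 5.5.7), and adverse event tables do not use dose (SAP 5.6.2). Treatment duration, dosing days, Week 12 maintenance dose and tablet-count compliance do not use the frequency code either.

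It is also fair to say that zero is right for some rows. Interruptions go on the same log, and a blanket ban on zero would credit drug not taken.

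None of this defends zero for a record with a positive dose, and the footnote's reason remains wrong for ONCE.

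**Conclusion.** The rule as written gives a wrong number for any positive-dose record with an affected code. The error can only be downward. The point is minor and conditional.

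Its size rests on an unknown count of records. Over the assumed range of 7 to 91 of 280 maintenance days, the affected participant's post-titration mean falls by 2.5% to 32.5%; 28 days give 10%, or 3,200 to 2,880 µg/day in the example. Cumulative dose falls by about 8% for 28 days. The percentages for the mean need a constant maintenance dose but do not depend on its level. A maintenance period shortened by early termination would make the same number of days a larger share. The ONCE code on Day 1 is wrong in principle and negligible in amount.

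The consequence stops at the descriptive summaries of cumulative and mean daily dose.

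**What to change.** Replace the zero rule in SAP 5.6.1, for records with a dose above zero, with the following:

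1. Count ONCE as one administration of the recorded dose. Query a ONCE record that spans several days.
2. If a frequency is still unresolved after querying, set total daily dose to missing and leave those days out of both numerator and denominator of the mean.
3. Report that participant's cumulative dose as incomplete, or bound it at one and two times the recorded dose per affected day.
4. State the number of affected records and participants.
5. Keep zero only for logged interruptions.

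This is a short SAP edit and a small programming change, with no effect on data collection or study conduct. The price is that a few participants may have an incomplete or bounded cumulative dose.
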